The participants who choose to consent and enroll in the study will then complete either the EEsAI (age 18 -60) or the PedsQL (age 6-17), both validated questionnaires that assess patient symptoms of EoE. Additionally, all study participants will have their initial Esophagogastroduodenoscopy (EGD) images evaluated via Endoscopic Reference Score (ERFS). This scoring system is a validated tool that has demonstrated moderate to good inter-observer variability. The PI for this protocol will be the physician who assigns a score to pre and post intervention images, in order to limit variations between graders. The 6-8 esophageal biopsies taken at initial EGD will be evaluated by pathology per routine protocol to provide primary diagnosis. Again to limit variation, there are two pathologists serving on this protocol as AIs that will be evaluating the specimens obtained during this research period. Each set of biopsies will then be evaluated by 1 of these 2 pathologists to record the number of eosinophils per high power field (HPF). Immunohistochemical staining on these biopsies for eotaxin-3 will be performed on the Ventana Ultra platform after stain optimization based on previously described protocols. Staining will be evaluated by 1 of 2 pathologists for intensity and percentage of cells staining (Allred scoring system). [name] will be performing research as a credentialed provider at WRNMMC Department of Pathology, although he is assigned to Joint Pathology Center.

The participants will be randomized into 2 groups: 1) omeprazole + swallowed fluticasone and 2) placebo + swallowed fluticasone. The placebo will replicate oral omeprazole. The study participants will be randomly assigned with concealment of allocation to one of the treatment groups, with each group having an equal number of participants (1:1 ratio).

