Each treatment group will be treated for 8 weeks. Therapy for the PPI + topical steroid group will be 40mg omeprazole by mouth twice daily and 880mcg swallowed fluticasone twice daily. Therapy for the placebo + topical steroid group will be a sham omeprazole capsule by mouth twice daily and 880mcg nebulized and swallowed fluticasone twice daily (total dosage 1760 mcg). Participants will be instructed to take omeprazole or placebo on an empty stomach each morning, at least 30 minutes prior to eating, but no more than 60 minutes. Participants will also be instructed to rinse mouth with water or brush teeth after taking fluticasone, but not swallow anything within 30 minutes after taking the medication. For study participants age 17 years and younger, the dose for fluticasone will be 440mcg given 2-4 times per day based on 2011 consensus guidelines.(1) The pediatric dose for omeprazole will be 2mg/kg/day divided twice daily, with max dose of 40mg per day.

Compliance will be checked via phone follow up at 4 weeks and in person at 8 weeks (completion of therapy) by asking patient to report number of pills remaining and number of actuations remaining on the MDI. Participants will be given enough medication to last the full 8 weeks of therapy. At the time of repeat endoscopy, patients will be instructed to bring their medications for a full count of remaining pills.

At the end of 8 weeks of therapy, participants will undergo repeat EGD, with re-evaluation of all markers completed at the start of therapy including esophageal eosinophilia, endoscopic assessment (EREFS), validated clinical questionnaire (EEsAI or PedsQL), and immunohistochemistry staining for eotaxin-3. EGDs will be performed to standard of care, with biopsies taken from the esophagus only.

Prior to the EGDs, all pediatric subjects will undergo the routine pre-op evaluations and physicals by Pediatric GI and anesthesia, which is standard of care. All subjects are required to fast beginning the night prior to the EGD which is also standard practice.

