The EGDs will be performed according to standard of care. All pediatric patients undergoing EGD for evaluation of symptoms consistent with abdominal pain, dysphagia, vomiting, poor weight gain, etc., have the same endoscopic investigation and biopsy specimens obtained, regardless of what is seen. It is also standard of care for all adult subjects presenting with symptoms suggestive of EoE (dysphagia, food impaction) to undergo upper endoscopic evaluation with esophageal biopsies. Biopsy specimens will be sent to pathology for standard histological examination. A single pathologist will be assigned to review all of the slides and corroborate the findings on any abnormal results.

EGDs will be performed using Olympus GIF140 or 160 endoscopes. Each subject will undergo all the standard pre-operative evaluations including physicals done by the pediatric GI provider and anesthesia. The type of sedation or general anesthesia will be based on the assessment by the anesthesia team responsible for the subject during the EGD. All pediatric patients undergoing an EGD will have the same endoscopic evaluation regardless of the indication for the procedure. It is standard practice to obtain biopsies from the duodenum, stomach and esophagus during the initial EGD, however, follow up EGDs will include only esophageal biopsies.

Esophageal biopsy specimens sent to pathology will be examined and reviewed by the pathologists. For each subject, the specific number of eosinophils per high power field (HPF) will be collected. As previously mentioned, 1 of 2 participating pathologists will be assigned to review all the slides, and corroborate the specific number of eosinophils. This data is also documented as part of the subjects routine care, and thus the results will be maintained in the AHLTA electronic record system as well. As an additional outcome measure, tissue eotaxin-3 level, will be measured independently by 1 of 2 pathologists on all subjects.

Assessment	Visit/Follow up Interval				
	Day of identification	Within 2 weeks of consent	Week 4	Week 8	Week 8-10
Screening/Informed consent /Discuss plan	X				
Randomization	X				
Demographics	X				
Pt completes clinical questionnaire	X				
Begin treatment	X				
PI/AI reviews initial endoscopy findings		X			

Path stain esophageal tissue for eotaxin-3		X			
Phone follow up for compliance check			X		
EGD				X	
Pt completes clinical questionnaire				X	
Path stain for eotaxin-3 on repeat biopsies					X

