PI/AI reviews repeat endoscopy findings					X

10.2 Data Collection:

Describe all the data variables, information to be collected, the source of the data, how the data will be operationally measured, and approvals needed for use of information from DoD databases

Method of Collection from Study Participants.

- EEsAI or PedsQL (approval received for research use) standardized symptom questionnaires, based on age of participant, will be used to assess participant symptoms prior to treatment.
- Initial Esophagogastroduodenoscopy (EGD) images will be evaluated via Endoscopic Reference Score (EREFS) by investigators.
- Biopsies taken at initial EGD will be evaluated by pathology for number of eosinophils per high power field (HPF) and tissue eotaxin-3 level.
- Compliance will be checked via phone follow up at 4 weeks, and in person at 8 weeks (completion of therapy) by asking patient to report number of pills remaining and number of actuations remaining on the MDI.
- Participants will be given enough medication to last the full 8 weeks of therapy.
- At the end of 8 weeks of therapy, participants will undergo repeat EGD, with re-evaluation of all markers completed at the start of therapy: EREFS, EEsAI or PedsQL, and tissue for number of eosinophils per HPF and eotaxin-3 staining.

Study variables

- a. Independent
 1. Standard therapy treatment group: Fluticasone topical steroid
 2. Intervention treatment group: Fluticasone topical steroid + PPI
- b. Dependent
 1. EEsAI/PedsQL

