14.0 Risks and Benefits

14.1 Risks of Harm:

Identify all research-related risks of harm to which the subject will be exposed for each research procedure or intervention as a result of participation in this study. Consider the risks of breach of confidentiality, psychological, legal, social, and economic risks as well as physical risks. Do not describe risks from standard care procedures; only describe risks from procedures done for research purposes

Research participants will not be exposed to any more risks than what are experienced by non-study patients being evaluated and treated for Eosinophilic Esophagitis. All interventions are within standard of care parameters in either treatment or control arm. It should be noted that there are risks associated with the EGD procedure to include bleeding, pain, infection, and intestinal perforation. There are also risks associated with the anesthetics used. However, patients who do not participate in the study would be subject to the same frequency and risks of EGD procedures.

14.2 Measures to Minimize Risks of Harm (Precautions, safeguards):

For each research procedure or intervention, describe all measures to minimize and/or eliminate risk of harms to subjects and study personnel

Safety Monitoring Plan

Participants will have cardiorespiratory monitoring throughout the endoscopic procedures, and will undergo pre procedure and post procedure monitoring per hospital protocol. The participant will receive a standard follow up call for biopsy results from the respective clinic, as is the standard of care for all patients who receive endoscopy. In addition, study participants will receive a telephone follow up 4 weeks after starting therapy.

Safety Analysis Plan

At the 4 week phone follow up, participants will be asked about any symptoms that have started since study treatment began. If worsening symptoms, patient will be brought in for a clinic visit to further evaluate ability to continue in trial.

14.3

Confidentiality Protections (for research records, data and/or specimens):

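### New symptoms are asked about only at the week-4 call; the week-8 visit has no such question and no by-arm safety summary is planned

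*Combined protocol and SAP*

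**What the plan says.** Section 10.1 fixes the exposure: "Each treatment group will be treated for 8 weeks". Section 14.2, under Safety Analysis Plan, provides one enquiry about new symptoms: "At the 4 week phone follow up, participants will be asked about any symptoms that have started since study treatment began". A clinic visit follows if symptoms are getting worse. No later enquiry of this kind is stated anywhere.

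The schedule table in 10.1 describes the week-4 contact only as "Phone follow up for compliance check". It has no adverse-event row at any visit, so even the week-4 question does not appear there.

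Week 8 is an in-person contact with listed content. Compliance is checked "in person at 8 weeks (completion of therapy) by asking patient to report number of pills remaining", together with the inhaler actuations left. Section 10.2 then lists "re-evaluation of all markers completed at the start of therapy: EREFS, EEsAI or PedsQL", plus the biopsy eosinophil count and eotaxin-3 staining. Section 10.1 describes the EEsAI and PedsQL as "both validated questionnaires that assess patient symptoms of EoE", and 11.6 analyses them as efficacy outcomes.

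The study spreadsheet described in 14.3 holds questionnaire scores, EREFS, histology and demographics. Neither it nor the table in 11.6 mentions adverse events.

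**The concern.** The one safety question comes at the midpoint of treatment, and nothing equivalent is specified for the second half. A subject who first develops a non-serious symptom after the call is not asked about it, although the same subject attends in person four weeks later.

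The trial is meant to inform whether the PPI should be kept on when swallowed fluticasone is started, a choice that 10.1 says standard care leaves open. Section 18.2 lists many possible untoward effects for each drug, and esophageal candidiasis is on both lists. If the combination shows a histologic benefit, readers will want a simple count of new symptoms by arm over the full 8 weeks. As written, the plan would give a count that is solicited for weeks 0-4, unsolicited afterwards, and not tabulated by arm. Answers not collected at week 8 cannot be reliably reconstructed later.

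**Working it through.** The plan states no safety figure to reproduce, so the first step is to read each contact for what it would detect after week 4.

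- Week-4 call (14.2): dedicated new-symptom question; covers weeks 0-4.
- Week-8 compliance check (10.1, 10.2): pill and actuation counts; no symptom question stated.
- Week-8 EEsAI or PedsQL (10.1, 10.2): described as measuring symptoms of the disease; not presented as an enquiry about new symptoms on study drug.
- Evaluation before the EGD (10.1): "Each subject will undergo all the standard pre-operative evaluations including physicals done by the pediatric GI provider and anesthesia". This is standard of care and is not described as adverse-event ascertainment.
- Week-8 EGD and biopsies (10.1): inspect the esophagus and could reveal a local finding; no recording rule is given.
- Call after the EGD (14.2): "The participant will receive a standard follow up call for biopsy results from the respective clinic"; no symptom question stated.
- Reporting rules (14.6, 16.1): routes and deadlines for events once known. The form's prompt in 16.1 asks how unexpected events will be identified, and the answer does not say.

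So the dedicated enquiry covers 28 of 56 treatment days (28/56 = 50%).

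The second step is an illustration of size. Inputs: 8 weeks of treatment (10.1), enquiry at week 4 (14.2), 50 subjects per arm (11.4). The 8-week risk q of a first onset is **assumed**, because the documents give none, and the hazard h is assumed constant.

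h = -ln(1 - q)/8, so the probability of no event by week 4 is exp(-4h) = (1 - q)^0.5, and by week 8 it is 1 - q.

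Risk of first onset in weeks 5-8 = (1 - q)^0.5 - (1 - q). Late share = that risk divided by q.

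For q = 10%: 0.9^0.5 = 0.9487; late risk = 0.9487 - 0.9000 = 0.0487; late share = 0.0487/0.10 = 48.7%; expected late subjects = 50 × 0.0487 = 2.4 of 5.

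| Assumed 8-week risk | Share of first onsets in weeks 5-8 | Expected late subjects per arm of 50 | Expected total per arm |
|---|---|---|---|
| 2% | 49.7% | 0.5 | 1.0 |
| 5% | 49.4% | 1.2 | 2.5 |
| 10% | 48.7% | 2.4 | 5.0 |
| 20% | 47.2% | 4.7 | 10.0 |
| 30% | 45.6% | 6.8 | 15.0 |

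The late share hardly depends on the assumed risk. The number of subjects depends on it almost entirely.

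**The case against.** The strongest reply is that week 8 is far from empty. Subjects who complete treatment have a pre-operative evaluation, a symptom questionnaire and an endoscopy of the organ where candidiasis would show. Serious, unexpected related and unanticipated events that become known must be reported (14.6, 16.1), and a Research Monitor reviews adverse events (5.2). The stated aim and hypothesis concern histology and symptoms, and 14.1 describes all interventions as within standard of care. Section 15.1 calls for a monitoring plan or board; the selection cannot be read in the text available, so a separate plan cannot be excluded.

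Most of this stands, and it limits the point. A reader might infer that only spontaneous reports cover weeks 5-8. That is too strong, because the scheduled clinical contacts could bring events up. What remains is that none of them is specified as an enquiry about new symptoms, and reporting rules act only on events already found.

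Three other inferences are tempting and unsupported:

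- *That the arms are ascertained unequally.* Both have the same contacts under double blinding, so no directional bias is shown.
- *That 8 weeks of PPI is a new exposure covered only in part.* Section 10.1 requires an 8-week PPI course before the initial EGD, and the active arm continues it. The contrast is continuing versus switching to sham, so weeks 0-8 are not the whole PPI exposure.
- *That events which build up with exposure are the ones lost.* The calculation assumes a constant hazard and cannot show this. Persistent events may well be present at the week-8 evaluation; late ones that resolve before it are the likelier loss.

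**Conclusion.** The point holds as a modest, easily repaired gap. No dedicated new-symptom question is specified after week 4, and no by-arm safety summary is planned. The likely loss is non-serious events with first onset in weeks 5-8, under-counted in both arms alike.

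Across assumed 8-week risks of 2% to 30%, about 50% to 46% of first onsets, or about 0.5 to 7 subjects per arm of 50, fall after the only enquiry. This rests on a constant hazard and on risks that the documents do not supply. It is an upper limit on what would be missed, because some late events will be volunteered or noticed at the week-8 contacts. The efficacy analyses are unaffected.

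**What to change.** 1. Ask the identical new-symptom question, in the same words and in both arms, at the existing week-8 visit. Asking it before the endoscopy keeps procedural complaints out of the count.
2. Show the question in the 10.1 schedule at weeks 4 and 8.
3. Add a field for the answers to the study dataset described in 14.3.
4. Add one descriptive row to 11.6: the number of subjects in each arm with any new symptom over weeks 0-8, with the number asked as denominator and no hypothesis test.

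This needs no new visit, no change in sample size and no change in clinical management. The cost is one question, one data field and a few more minor events to record. The by-arm comparison will be imprecise: even with no event among 50 subjects, the one-sided 95% upper limit for the risk is 1 - 0.05^(1/50) = 5.8%. The row should therefore be read as description only.

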15.0 Study Monitoring

15.1 Your study requires either Data and Safety Monitoring Plan (DSMP) or a Data and Safety Monitoring Board (DSMB).

- DSMP
- DSMB
- Both
- Not Applicable

16.0 Reportable Events

16.1 Reportable Events:

Consult with the research office at your institution to ensure requirements are met

- Describe plans for reporting expected adverse events. Identify what the expected adverse events will be for this study, describe the likelihood (frequency, severity, reversibility, short-term management and any long-term implications of each expected event)

- Describe plans for reporting unexpected adverse events and unanticipated problems. Address how unexpected adverse events will be identified, who will report, how often adverse events and unanticipated problems will be reviewed to determine if any changes to the research protocol or consent form are needed and the scale that will be used to grade the severity of the adverse event

Reportable Events include adverse events (AE), serious adverse events (SAE), unanticipated problems involving risks to subjects or others (UPIRTSO), and protocol deviations as defined by the WRNMMC IRB Handbook.

UPIRTSOs, are unexpected AEs and SAEs, in the opinion of the PI, are possibly related to participation AND places subjects or others at a greater risk of harm that was previously known or recognized in the protocol and must be reported to the IRB and Research Monitor via email or telephone within 24 hours of discovery and a written follow up report within 5 business days.

Expected reportable events and events that are not related to study participation are reported on the Continuing Review (CR) Progress Report. CR is generally performed on a 12-month cycle. More frequent Progress Reports may be required at the discretion of the IRB.

When a deviation occurs, the investigator shall report the occurrence to the IRB. The investigator is required to make the determination whether the deviation meets the criteria for an unanticipated problem involving risks to subjects or others. The IRB Chair or IRB staff member shall also make the determination if the protocol deviation meets the definition of an unanticipated problem involving risks to participants or others. If the IRB Chair or IRB Staff member determines and documents that the deviation is an unanticipated problem involving risks to subjects or others or the deviation resulted from serious or continuing noncompliance, the IRB staff member shall place the deviation on the agenda of the next available IRB meeting for review. If the IRB Chair or IRB Staff member determines and documents that the deviation is not an unanticipated problem involving risks to subjects or others, the IRB Chair or staff member shall acknowledge the submission and complete the review through an administrative review procedure. Deviations that are determined to be minor as defined by the WRNMMC IRB Handbook are reported on the Continuing Review (CR) Progress Report.

As a reminder, according to DoDI 3216.02 (November 8, 2011), the IRB shall approve an independent research monitor by name for all DoD-conducted research involving human subjects, determined by the IRB to involve more than minimal risk to human subjects. Additionally, the research monitor may be identified by an investigator or appointed by an IRB or Institutional Official (IO) for research involving human subjects determined to involve minimal risk.

The research monitor may perform oversight functions and will report their observations to the IRB or a designated official. The research monitor may discuss the research protocol with the investigators, interview human subjects, and consult with others outside of the study about the research. The research monitor shall have the authority to stop a research protocol in progress, remove individual subjects from a research protocol, and take whatever steps are necessary to protect the safety and well-being of human subjects until the IRB can assess the monitor's report. Research monitors shall have the responsibility to promptly report their observations and findings to the IRB or other designated official. The research monitors shall have expertise consonant with the nature of risk(s) identified within the research protocol, and they shall be independent of the team conducting the research involving human subjects

17.0

Equipment/non-FDA Regulated Devices

17.1 Does the study involve the use of any unique non-medical devices/equipment?

Yes No

18.0

FDA-Regulated Products

18.1 Will any drugs, dietary supplements, biologics, or devices be utilized in this study?

- Drugs
- Dietary Supplements
- Biologics
- Devices
- N/A

18.2 Drugs, Dietary Supplements and Biologics/Vaccines details:

- Are drug(s) in this research being used in accordance to the approved labeling?
- Are drug(s) in this research being used in a manner other than its approved labeling?

Enter Dietary Supplements and Biologics/Vaccines in the Drug Information table. Complete all relevant fields in the table ("Protocol Drug Details" screen). If the question is not relevant, leave the question blank and/or do not change the default selection.

View Details	Drug Name	FDA Approved	A new drug or a new use of approved drug:	IND Number
	Trade Drug Name: FLUTICASONE Generic Drug Name: PROPRIONATE Investigational Drug Name:	Yes	No	

Trade Drug Name:	FLUTICASONE PROPRIONATE
Generic Drug Name:	
Investigational Drug Name:	
Identify the name of the manufacturer or source of investigational drug/biologic:	WRNMMC Research Pharmacy
Is the drug supplied at no cost?	Yes
Is the Drug FDA Approved:	Yes
Is this a new drug or a new use of an already approved drug	No
Is an IND necessary	No
IND Number	
Who holds the IND:	N/A
IND details:	
If FDA Approved and an IND is not required, Please provide a rationale for exemption:	Fluticasone is utilized off-label in the treatment of EoE. Nebulized and swallowed (topical)fluticasone treatment for EoE is accepted as a standard medical practice and is recommended as a first line treatment for EoE in both adult and pediatric consensus statements.(1, 16, 17) This study meets exemption criteria under 312.2b.1 under 21 CFR 312 and is not subject to FDA reporting requirements.
Are you currently using this IND in another research project?	No
If yes, list the IRB Number(s):	
Dose Range:	
Frequency:	BID

Route of administration:	Swallowed
Will the investigational pharmacy be dispensing?	No
If the source is not a FDA licensed facility, provide details regarding the purity, quality, stability and sterility of the investigational drug/biologic:	
Identify who will be preparing the investigational drug/biologic for administration and describe in detail how it will be prepared:	Preparation will be in accordance with standard practices for WRNMMC pharmacy. No special handling is required.
Indication(s) under Investigation:	
Where will the drug be stored	WRNMMC pharmacy, in accordance with standard medication storing and dispensing practices.
Drug Storage Restrictions (including temperature, etc.):	As per indications on medication labeling.
Administration Instructions:	18 years old and above: swallow 4 puff of 220mcg fluticasone twice daily. Do not eat or drink within 30 minutes of swallowing. 6-17 years old: dose for fluticasone will be 220mcg given 4-8 times per day based on age, as recommended by expert consensus guidelines.
Possible Untoward Effects, Their Symptoms & Treatment:	Fatigue, malaise, headache, oropharyngeal candidiasis, arthralgia, arthritis, musculoskeletal pain, sinus infection, sinusitis, upper respiratory tract infection, throat irritation, nasal congestion, nasopharyngitis, rhinitis, bronchitis, hypertension, subarachnoid hemorrhage, generalized pain, voice disorder, procedural pain, skin rash, pruritus, nausea and vomiting, viral gastrointestinal infection, gastrointestinal distress, gastrointestinal pain, toothache, malignant neoplasm of breast, influenza, abscess, muscle injury, back pain, herniated disk, cough, hoarseness, pharyngitis, upper respiratory tract inflammation, oropharyngeal pain, allergic rhinitis, fever, accidental injury, amputation, adrenocortical insufficiency, aggressive behavior, allergic skin reaction, aphonia, bacterial infection, bacterial reproductive infection, behavioral changes (very rare: includes hyperactivity and irritability in children), blepharoconjunctivitis, bronchospasm (immediate and delayed), cataract (long-term use), cholecystitis, Churg-Strauss syndrome, conjunctivitis, cranial nerve palsy, cushingoid appearance, decreased bone mineral density (long-term use), decreased linear skeletal growth rate (children and adolescents), dental caries, dental discoloration, depression, dermatitis, drug toxicity, eosinophilia, esophageal candidiasis, exacerbation of asthma, folliculitis, fungal infection, glaucoma (long-term use), hematoma, HPA-axis suppression, hypercorticism, hyperglycemia, hypersensitivity reaction (immediate and delayed; includes ear, nose, and throat allergic disorders, anaphylaxis, angioedema, bronchospasm, hypotension, skin rash, urticaria), increased intraocular pressure (long-term use), inflammation (musculoskeletal), keratitis, migraine, oral mucosa ulcer, osteonecrosis (especially with current or past use of systemic steroids), osteoporosis, paradoxical bronchospasm, photodermatitis, pneumonia, polyp (ear, nose, throat), pressure-induced disorder, soft tissue injury, urinary tract infection, vasculitis, viral skin infection. Treatment: discontinue use of medication.
Potential or Actual Antidotes for Excessive or Adverse Drug Effect:	None
Contraindications and Interactions, If Known:	Hypersensitivity to fluticasone.

Investigators Authorized to Prescribe:	Principal investigator and all associate investigators.		
	Trade Drug Name: Omeprazole Generic Drug Name: Investigational Drug Name:	Yes	No
Trade Drug Name:	Omeprazole		
Generic Drug Name:			
Investigational Drug Name:			
Identify the name of the manufacturer or source of investigational drug/biologic:	WRNMMC Research Pharmacy		
Is the drug supplied at no cost?	Yes		
Is the Drug FDA Approved:	Yes		
Is this a new drug or a new use of an already approved drug	No		
Is an IND necessary	No		
IND Number			
Who holds the IND:	N/A		
IND details:			
If FDA Approved and an IND is not required, Please provide a rationale for exemption:	This study meets exemption criteria under 312.2b.1 under 21 CFR 312 and is not subject to FDA reporting requirements.		
Are you currently using this IND in another research project?	No		
If yes, list the IRB Number(s):			
Dose Range:			
Frequency:	BID		
Route of administration:	PO		
Will the investigational pharmacy be dispensing?	No		
If the source is not a FDA licensed facility, provide details regarding the purity, quality, stability and sterility of the investigational drug/biologic:			
Identify who will be preparing the investigational drug/biologic for administration and describe in detail how it will be prepared:	Preparation will be in accordance with standard practices for WRNMMC pharmacy. No special handling is required.		
Indication(s) under Investigation:	N/A		
Where will the drug be stored	WRNMMC pharmacy, in accordance with standard medication storing and dispensing practices.		
Drug Storage Restrictions (including temperature, etc.):	As per indications on medication labeling.		
Administration Instructions:	18 years old and above: take one 40mg capsule or tab by mouth twice daily. 6-17 years old: 2mg/kg/day divided twice daily, with max dose of 40mg per day.		

Possible Untoward Effects, Their Symptoms & Treatment:	Headache, dizziness, skin rash, abdominal pain, diarrhea, nausea, flatulence, vomiting, acid regurgitation, constipation, back pain, weakness, upper respiratory infection, cough, abdominal swelling, abnormal dreams, aggression, agranulocytosis, allergic reactions, alopecia, anaphylaxis, anemia, angina pectoris, angioedema, anorexia, apathy, arthralgia, atrophic gastritis, benign gastric polyps, blurred vision, bone fracture, bradycardia, bronchospasm, chest pain, cholestatic hepatitis, Clostridium difficile-associated diarrhea (CDAD), confusion, depression, dermatitis, diplopia, drowsiness, epistaxis, erythema multiforme, esophageal candidiasis, fecal discoloration, gastroduodenal carcinoids, glycosuria, gynecomastia, hallucinations, hematuria, hemolytic anemia, hepatic disease (hepatocellular, cholestatic, mixed), hepatic encephalopathy, hepatic failure, hepatic necrosis, hepatitis, hepatocellular hepatitis, hepatotoxicity (idiosyncratic), hyperhidrosis, hypersensitivity, hypertension, hypocalcemia, hypoglycemia, hypokalemia, hypomagnesemia, hyponatremia, increased gamma glutamyl transferase, increased serum alkaline phosphatase, increased serum bilirubin, increased serum creatinine, increased serum transaminases, insomnia, interstitial nephritis, irritable bowel syndrome, jaundice, leg pain, leukocytosis, leukopenia, malaise, microscopic colitis, microscopic pyuria, mucosal atrophy (tongue), muscle cramps, myalgia, myasthenia, nervousness, neutropenia, ocular irritation, optic atrophy, optic neuritis, optic neuropathy (anterior ischemic), osteoporosis-related fracture, pain, palpitation, pancreatitis, pancytopenia, paresthesia, peripheral edema, petechiae, photophobia, pneumonia, proteinuria, pruritus, psychiatric disturbance, purpura, sleep disturbance, sore throat, Stevens-Johnson syndrome, stomatitis, tachycardia, testicular pain, thrombocytopenia, toxic epidermal necrolysis, tremor, urinary tract infection, urticaria, weight gain, xeroderma, xerophthalmia, xerostomia. Treatment: Discontinue medication.
Potential or Actual Antidotes for Excessive or Adverse Drug Effect:	Discontinue medication.
Contraindications and Interactions, If Known:	Hypersensitivity to omeprazole or its components.
Investigators Authorized to Prescribe:	Principal investigator and all associate investigators.

18.4 Reporting Requirements for FDA-regulated research under IND and IDE:

Describe the process for complying with FDA regulatory requirements for adverse event reporting and adverse device effects reporting to the sponsor

N/A. This study meets exemption criteria under 312.2b.1 under 21 CFR 312 and is not subject to FDA reporting requirements.

18.5 Sponsor (organization/institution/company):

N/A

If applicable, provide sponsor contact information:

